1.4. Summary of clinical human data

To date, a total of 79 healthy male volunteers have been exposed to the study treatment: either emodepside Liquid Service Formulation (LSF) solution or immediate release (IR) tablets (dose range 1.0–40 mg LSF solution, and doses of 5 mg and 20 mg tablets; 59 volunteers) or placebo (20 volunteers). Volunteers received the treatment in fasted conditions, or, for the 8 subjects of Cohort 9 (receiving 10 mg LSF solution or placebo), after a high-fat, high calories breakfast.

This study was divided into 2 parts: part 1 with cohorts 1 to 8 including 63 subjects (47 exposed to emodepside) and part 2 with cohorts 9 and 10 including 16 subjects (12 exposed to emodepside).

Based on preliminary data, maximum exposure was observed with the 40 mg LSF solution (Cohort 8), with a mean C_{max} of 612 ng/mL and AUC of 4,315 ng.h/mL. So far, based on unblinded safety data from Part 1 of the study, those doses have been safe and tolerance was acceptable. Based on an unblinded review of the safety data, total number of subjects with at least one Treatment Emergent Adverse Events (TEAEs) are summarised below by System Organ Class (SOC).

Based on preliminary data, across all treatments within Part 1 (Cohorts 1-8), no serious AEs were reported. Overall, 53 non-serious TEAEs were reported by 31 out of the 63 subjects (49%), of which 45 non-serious TEAEs reported by 25 out of the 47 subjects (53%) exposed to emodepside and 8 non-serious TEAEs reported by 6 out of the 16 subjects (37%) exposed to placebo. All TEAEs (related or not) were mild or moderate in severity. All the treatment-related TEAEs resolved spontaneously within less than 24 h and without treatment.

A total of 14 subjects exposed to emodepside (22.2%) experienced 20 TEAEs that were considered by the Investigator to be related to emodepside treatment. In addition 4 TEAEs, reported in 3 subjects exposed to placebo, were assessed as related to treatment. All TEAEs, whether related or not, were mild or moderate in severity. The most frequently reported TEAEs were eye disorders and nervous system disorders.

All the treatment-related TEAEs resolved spontaneously within less than 24 h and without treatment.

Table 1: Total number of subjects with at least one TEAE (unblinded Cohorts 1 to 8 – by SOC)

SOC	Placebo		Emodepside									Total n=63 (%)

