receiving placebo reported dry eye (n=1). All eye disorders AEs were of mild to moderate intensity, resolved spontaneously (without treatment), and were more frequently reported with highest dose (40 mg). Among them, the AEs of blurred vision, photophobia (“Increased ocular light sensitivity”), visual impairment (“distorted contrast perception”, “distorted colour perception”) reported by 8 out of 47 subjects receiving emodepside were considered as treatment-related by the Investigator. Also of note, at the highest dose (40 mg), lightheadedness (n=1), dizziness (n=1) or headache (n=1) were reported concomitantly to blurred vision.

None of the volunteers met any of the protocol-specified withdrawal criteria and overall tolerability to emodepside has been acceptable up to 20 mg. The presence of post-dose visual disturbances in subjects of Cohort 8 receiving either 40 mg solution or placebo may warrant some concern and escalation was stopped at this dose level.

The pharmacokinetic results obtained so far show that T_{max} for the LSF solution is consistently about 1 h post-dose when fasted. Mean C_{max} and AUC for the LSF solution have been roughly dose-proportional, with low to moderate inter-individual variability. The plasma half-life during the first 24 h is very short for a single dose of emodepside. After 3, 7, 16 and 47 h the maximum plasma concentration is reduced to 50%, 25%, 12.5% and 6.25% respectively. Terminal plasma half-life is 523 h. Although data of Cohort 9 (which was treated with a single dose of emodepside with food) are still under review, administration of the LSF of 10 mg with a high fat, high-calorie meal resulted in a clinically relevant food effect with a reduction of AUC to ~67%, C_{max} to 42% and a delay of the T_{max} up to 2.33 h. Therefore, the recommendation of administration of the emodepside (LSF) under fasted conditions is given.

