1.5. Assessment and management of risk

The factors taken into account in the assessment of risk to subjects in this study are as follows:

- The planned daily doses of emodepside have been administered to humans as single doses and were well tolerated. Based on the first-in-human clinical study, overall tolerability to emodepside has been acceptable up to 20 mg. Post-dose visual disturbances were observed more frequently at 40 mg, and although these visual and nervous system disturbances were considered non-serious and mild in intensity, dose escalation was stopped at this dose level. All visual disturbances were transient in nature and resolved spontaneously within 24 h, and without treatment.
- During the study, the dose will be increased only if the PK, safety and tolerability of the previous dose is acceptable and if the investigator and sponsor's medical representative agree that it is appropriate to give a higher dose. The next planned dose level may be reduced, or a dose level may re-tested or an intermediate dose level selected, based on emerging data. The total daily dose will not exceed 20 mg emodepside (as LSF solution at a concentration of 1 mg/mL).
- Subjects will undergo a comprehensive ophthalmology assessment at screening and will be excluded from the study if any ocular pathology is detected. Additional ophthalmology assessments will be performed during the study, if clinically indicated.
- Subjects will undergo a full neurological assessment at screening, Day 0 and at discharge from the ward in order to detect and assess any neurological disorder or change.
- In the first-in-human trial (DNDI-EMO-01), emodepside was shown to undergo bi-phasic elimination with a dominant half-life ($t_{1/2\ 0-24}$) estimated at approximately 11 h, and terminal half-life ($t_{1/2\ 0-\infty}$) over 520 h. In order to comprehensively assess safety parameters over this period, volunteers will be followed up until Day 120.

2. Study Objectives and Endpoints

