2.2.3. Secondary Endpoint(s)

Pharmacokinetic Variables:

Emodepside plasma concentration–time data will be used to derive the following PK parameters of emodepside:

- After the first dose of emodepside (Day 0):
 - Main PK parameters:
 - Cohorts 1 & 2: AUC_{24} , AUC_{24}/D , C_{max} , C_{max}/D
 - Cohort 3: AUC_{12} , AUC_{12}/D , C_{max} , C_{max}/D
- After multiple doses of emodepside (Day 9):
 - Main PK parameters:
 - Cohorts 1 & 2: AUC_{∞} , AUC_{∞}/D , AUC_{24} , AUC_{24}/D , $C_{max,ss}$, $C_{max,ss}/D$
 - Cohort 3: AUC_{∞} , AUC_{∞}/D , AUC_{12} , AUC_{12}/D , $C_{max,ss}$, $C_{max,ss}/D$
- Accumulation ratios $RA(C_{max})$ and $RA(AUC_{tau})$ will be calculated
- C_{trough} will be derived from the concentration data (Days 1–9).

The above parameters may be calculated for the metabolites of emodepside, as appropriate.

Pharmacodynamic Variables:

- Time-matched profiles of glucose, glucagon, insulin, and cortisol
- Oral glucose tolerance test (OGTT)

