- on Day 0: before and at 1, 2, 3, 4, 6, 8 and 12 h after the morning dose
 - on Days 1–8: before the morning dose
 - on Day 9: before and at the following times after the morning dose: 0.5, 1, 2, 3, 4, 6, 8, 12, 24, 36 (Day 10), 48 (Day 11), 72 (Day 12), 96 (Day 13) and 120 h (Day 14)
 - at outpatients visits on Days 17, 20, 23 and 27 (± 2 days), and long-term follow-up visits (Days 60, 90 and 120 ± 2 days)
12. Blood samples for assay of emodepside in plasma will be taken:
- on Day 0: before and at 0.25, 0.5, 1, 1.5, 2, 2.5, 3, 4, 6, 8, 12, and 15 h after the morning dose
 - on Days 1–8: before the morning dose
 - on Day 9: before and at the following times after the morning dose: 0.25, 0.5, 1, 1.5, 2, 2.5, 3, 4, 6, 8, 12, 15, 24, 36 (Day 10), 48 (Day 11), 72 (Day 12), 96 (Day 13) and 120 h (Day 14)
 - at outpatients visits on Days 17, 20, 23 and 27 (± 2 days), and at Follow-up (Day 30 ± 2 days)
- Subjects should rest in the supine position for 10 minutes before blood is drawn (if possible).
13. Blood samples for assay of metabolites of emodepside in plasma will be taken:
- on Day 0: before and at 0.25, 0.5, 1, 1.5, 2, 2.5, 3, 4, 6, 8, 12, and 15 h after the morning dose
 - on Day 9: before and at 0.25, 0.5, 1, 1.5, 2, 2.5, 3, 4, 6, 8, 12, and 15 h after the morning dose
14. Urine for assay of emodepside and its metabolites may be collected at the following time points:
- On Day 0: from 0–4, 4–8, 8–12 and 12–24 h after the morning dose
 - On Day 9: from 0–4, 4–8, 8–12 and 12–24 h after the morning dose
15. Blood and urine samples for clinical laboratory safety tests (haematology, biochemistry, coagulation & urinalysis) will be taken: at Screening Visit 1; on Day –1 (–24 h before the morning dose on Day 0); before the morning dose on Day 0; before the morning dose on Days 1, 5 and 8; before, 24 h (Day 10) and 120 h after the morning dose on Day 9 (Day 14); at the Day 23 outpatient visit (± 2 days); at Follow-up (Day 30 ± 2 days); and at long-term follow-up (Days 60, 90 and 120 ± 2 days).
- Subjects should rest in the supine position for 10 minutes before blood is drawn (if possible).
16. Serology tests will comprise HIV 1 & 2, hepatitis B & C, and HbA1c
17. Blood samples for measurement of leptin and prolactin will be taken at Screening Visit 1 and before the morning dose on Day 9.
18. Subjects will be admitted to the ward on Day 119, before the Day 120 long-term follow-up visit.

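### Emodepside PK sampling stops at Day 30, less than one terminal half-life after the last dose, so Day 9 AUC-infinity is expected to break the SAP's 20% extrapolation rule

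*Protocol*

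**What the plan says.** Protocol Section 5.1, footnote 12, schedules the late plasma samples for emodepside "at outpatients visits on Days 17, 20, 23 and 27 (± 2 days), and at Follow-up (Day 30 ± 2 days" and none after that. The SAP's copy of the schedule has the same footnote. Safety laboratory blood (footnote 15) goes further: "at Follow-up (Day 30 ± 2 days); and at long-term follow-up (Days 60, 90 and 120 ± 2 days".

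Protocol 1.4 reports from the first-in-human study: "Terminal plasma half-life is 523 h". It describes the earlier decline as "After 3, 7, 16 and 47 h the maximum plasma concentration is reduced to 50%, 25%, 12.5% and 6.25% respectively". Protocol 1.5 says "emodepside was shown to undergo bi-phasic elimination with a dominant half-life" of about 11 h, and uses the long terminal phase to justify the length of follow-up: "In order to comprehensively assess safety parameters over this period, volunteers will be followed up until Day 120".

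In Protocol 2.2.3, under "After multiple doses of emodepside (Day 9"), AUC-infinity and AUC-infinity/D head the main PK parameters for all three cohorts.

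SAP Appendix B 1.2 sets three rules:
- AUC-infinity is reported when less than 20% of it is extrapolated.
- Profiles above 20% may be included only if at least 80% of profiles are below 20%.
- Above 40%, the value is not to be used without a specific justification in the study report.

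Appendix B 1.3 selects the terminal slope (lambda-z) by the largest adjusted R-squared over the last three or more points, and restricts the fit to points judged to lie on the terminal decline.

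**The concern.** A schedule that ends before one terminal half-life has passed cannot support an area to infinity under rules this strict. If most profiles exceed 20%, AUC-infinity and AUC-infinity/D drop out of routine reporting in both planned reports (Cohorts 1-2, and Cohort 3) and survive only by exception. The exploratory terminal half-life and MRT-infinity would be poorly estimated. The protocol keeps subjects until Day 120 because of this half-life and takes blood at those visits, but does not assay emodepside in it. A tail that is not sampled then cannot be recovered later.

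**Working it through.** **1. Is Day 30 really the last sample?** Footnote 12 gives 13 samples (Day 0) + 8 (Days 1-8) + 19 (Day 9 to 120 h) + 5 (Days 17, 20, 23, 27, 30) = 45. The blood-volume table in Protocol 8.4.4 also has 45. Sampling on Days 60, 90 and 120 as well would need 48. Section 8.3.10 lists PK blood under a heading that includes the late visits, but it is a some-or-all list that defers to Section 5. Section 8.4.1 gives only a time window. Neither schedules a later sample.

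**2. Time covered.** The last dose is on the morning of Day 9 in every cohort. (30 − 9) × 24 = 504 h, and 504/523 = 0.96 half-lives. If the whole area were terminal phase, the share beyond Day 30 would be 2^(−504/523) = 51.3%, an upper bound.

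**3. Projection from the stated decline.** Work in units of the single-dose Cmax, with a linear rise to 1 h, log-linear segments through the stated points, and a 523 h half-life from 47 h.
- Area 0-47 h: 0.50 + 1.44 + 1.44 + 1.62 + 2.80 = 7.80.
- Area after 47 h: 0.0625 × 523/ln 2 = 47.16. Total: 54.96.
- Area after 24 h: 54.96 − 5.92 = 49.04.
- Area after 504 h: 47.16 × 2^(−457/523) = 25.73.

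Superpose ten once-daily doses and count from the Day 9 dose:
- Total: 54.96 (last dose) + 49.04 (the dose before) + 337.97 (the eight earlier doses, sum of 47.16 × 2^(−(24i − 47)/523) for i = 2 to 9) = 441.97.
- After Day 30: sum of 25.73 × 2^(−24i/523) for i = 0 to 9 = 223.96.
- Share: 223.96/441.97 = **50.7%**. For 19 twelve-hourly doses it is **50.9%**.

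**4. A deliberately low end.** Use a bi-exponential with half-lives of 11 h and 523 h, set to 6.25% at 47 h (46 h after the peak). The terminal coefficient is (0.0625 − 2^(−46/11)) / (2^(−46/523) − 2^(−46/11)) = (0.0625 − 0.0551)/(0.9409 − 0.0551) = 0.84% of Cmax. The share after Day 30 is **37.1%** (once daily) or **39.5%** (twice daily). This curve predicts 39% of Cmax at 16 h, against the stated 12.5%, so it understates the tail.

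**5. Intermediate shapes.** Starting the 523 h phase at 120 h or 240 h gives 45-50%. A three-exponential with a terminal coefficient of 1% of Cmax gives 41-42%. Across all five curves and the ±2-day window the range is 35-54%. The share falls to 20% only if the terminal phase starts at 0.16-0.21% of Cmax per dose, and to 40% at 0.83-1.13%. Equivalently, on the step 3 curve, the half-life would have to be below about 220 h (20%) or 390 h (40%).

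**6. Does the stated AUC contradict this?** Protocol 1.4 gives a mean Cmax of "612 ng/mL and AUC of 4,315 ng.h/mL", and 4,315/612 = 7.05 × Cmax. The stated decline reaches that by about 36 h (5.9 at 24 h, 7.9 at 48 h). The figure therefore fits a partial AUC and does not bound the tail.

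**7. What the SAP rule would see.** The rule applies to the estimated share, so the SAP's lambda-z procedure was simulated on the planned sampling times. Residual error is an assumption.

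| Lambda-z fit, Day 30 last sample | Error | Profiles >20% | Profiles >40% | Median half-life |
|---|---|---|---|---|
| Automated search | 10% | 89-100% | 14-84% | 330-470 h |
| Day 17 onward only | 10% | 99.8-100% | 35-90% | 474-535 h |
| Automated search | 20% | 45-97% | – | – |
| Day 17 onward only | 20% | 92-100% | – | – |

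The automated search tends to return a half-life below the true 523 h. The later fit is nearly unbiased but wide (5th-95th percentile 327-1087 h).

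**8. Later samples.** If levels are quantifiable, the share beyond the last sample is 14-20% at Day 60, about 6-8% at Day 90 and 2-3% at Day 120. With Days 60 and 90 added, median half-life is 520-525 h (464-596 h), and estimated/true AUC-infinity runs from 0.95 to 1.07 instead of 0.69 to 1.67.

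**The case against.** The main counter-argument is about weight. The primary endpoint is safety, the study is exploratory, and the PK quantities used for escalation do not need the tail. The SAP's formulas for CLss/F and Day 9 Vz/F appear to use the dosing-interval AUC, and the SAP already foresees high extrapolation and derives the percentage. All of this stands and limits the consequence. It does not make an exception a sensible expected route for a parameter listed as main.

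A second argument is that a short estimated half-life could bring profiles under 20%. In the most favourable case examined (only a quarter of the 47 h level terminal, an assumed 100 h intermediate phase, 10% error), 37% of once-daily profiles exceed 20%. The 80% condition needs at least 10 of 12 profiles, or 5 of 6, below 20%. With probability 0.63 per profile, the binomial chance is 12% for 12 profiles and 28% for 6. Failure remains the likelier result, and a pass would rest on a biased half-life.

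Third, AUC-infinity could be made exploratory at no cost. That is a coherent fallback, but it gives up the parameter instead of measuring it. Whether dividing by the administered dose makes AUC-infinity/D meaningful after repeated dosing is a separate question that later sampling does not answer.

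Finally, the benefit depends on an unstated LLOQ. This is correct, and the size of that dependence is given with the fix.

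**Conclusion.** The concern holds. On the protocol's own half-life and decline figures, about 37-51% of Day 9 AUC-infinity lies beyond the last planned sample, and the SAP's 20% rule with its 80%-of-profiles condition is expected to fail in both reports. Whether the 40% limit is passed depends on tail shape and assay error, which the documents do not settle. The 0.96 half-lives and the 51% upper bound need only the stated half-life and schedule. The lower end rests on an assumed curve, and the profile percentages on assumed residual error. Adding an assumed 25% between-subject CV in half-life leaves the conclusion unchanged: at 10% error, 87-100% of once-daily profiles exceed 20%, falling to 1-3% with Days 60 and 90 sampled and quantifiable. This should be fixed, but it does not touch the safety objective or the escalation rules.

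**What to change.** Add a 3 mL emodepside sample to the blood draws already scheduled on Days 60 and 90, and on Day 120 if levels are expected to be quantifiable. Day 60 alone is not enough: under the log-linear curves 18-43% of profiles would still exceed 20%.

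Changes to the text:
- Protocol footnote 12 and the SAP schedule: add the new days.
- Protocol 8.4.4: emodepside PK from 45 samples/135 mL to 47/141 mL, or 48/144 mL with Day 120. Update the total too; the table now gives 548 mL and the text 538.5 mL.
- Protocol 8.3.10 and 8.4.1: say whether PK samples are taken at the long-term visits.
- State the LLOQ.

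Cost: 36 extra assays in the 18 active subjects, or 54 with Day 120 (72 if placebo samples are assayed as well), and 6-9 mL more blood per subject, within the 50 mL allowance in 8.4.4. No new visit or venepuncture is needed, and 8.4.1 allows added time points with the Sponsor's approval.

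The return depends on the assay, because post-peak values below the LLOQ are treated as missing. Scaling from 612 ng/mL at 40 mg, projected mean levels on Days 60 and 90 are 1.1-8.7 and 0.4-3.4 ng/mL in Cohort 1, and 4.2-33 and 1.6-12.8 ng/mL in Cohort 3. Profiles still above 20% after adding Days 60 and 90 (assumed 10% error, 30% between-subject CV):

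| LLOQ (ng/mL) | Cohort 1 | Cohort 2 | Cohort 3 |
|---|---|---|---|
| 0.5 | 0-4% | ≤0.2% | ≤0.2% |
| 1 (only an example in a SAP listing shell) | 0-44% | 0-4% | ≤0.2% |
| 2 | 2-92% | 0-41% | 0-7% |

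If the LLOQ makes late levels unmeasurable in a cohort, say so and move AUC-infinity to the exploratory list for that cohort.

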5.2. Table 3: Schedule of events expanded view: pre-dosing period

Procedure	Pre-dosing period													
	Day -2				Day -1									
	-48 h	-47 h	-46 h	-44 h	-24 h	-23.5 h	-23 h	-22.5 h	-22 h	-21 h	-20 h	-18 h	-16 h	-12 h
Short physical examination ²					X		X		X		X			X
Short neurological examination ⁴					X		X		X		X			X
Oral Glucose Tolerance Test (OGTT) ⁶	X	X	X	X										
Glucose, insulin, glucagon and cortisol ⁷					X		X		X		X			X
12-lead safety ECGs ⁹					X	X	X	X	X	X	X		X	X
Vital signs ¹⁰					X	X	X	X	X	X	X		X	X
AE monitoring ¹¹					X		X		X	X	X	X	X	X
Laboratory safety tests ¹⁵					X									

5.3. Table 4: Schedule of events expanded view: first dosing day

Procedure	First dosing day (Day 0)													
	0 h	0.25 h	0.5 h	1 h	1.5 h	2 h	2.5 h	3 h	4 h	6 h	8 h	12 h	15 h	24 h
Short physical examination ²	X			X		X			X			X		
Full neurological examination ³	X													
Short neurological examination ⁴				X		X			X			X		
Glucose, insulin, glucagon and cortisol ⁷	X			X		X			X			X		
Administration of emodepside ⁸	X											X*		
12-lead safety ECGs ⁹	X		X	X	X	X		X	X		X	X		
Vital signs ¹⁰	X		X	X	X	X		X	X		X	X		
AE monitoring ¹¹	X			X		X		X	X	X	X	X		
PK of emodepside in plasma ¹²	X	X	X	X	X	X	X	X	X	X	X	X	X	

6. Enrolment procedures

The study will be carried-out in healthy male subjects at the following Phase 1 unit:

Hammersmith Medicines Research Limited,
[name]

The Investigator or his/her delegate should document the date when informed consent was obtained (Screening), screening dates, subject initials, Screening Number, date of eligibility and inclusion in the study (Enrolment), Subject Number (when Randomised – received treatment) or reason for not enrolling (Screen Failure) or not being randomised, whenever applicable.

Screening should occur between 3 and 28 days before the intended initiation of treatment: detailed procedures are described in Section 8: Study Assessments.

All subjects must give written consent (see Sections 8.1 and 15.1 for Informed Consent Procedures) to participate in this trial. Consent for screening evaluations may be obtained using the information and consent form for the HMR healthy volunteer panel, which was originally approved by London – Brent Research Ethics Committee (REC) and has subsequently been approved by the Generic Document Review Committee. The trial-specific information and consent form will be signed by the subject either before any screening evaluation or after the Investigator assesses the eligibility of the subject for the trial, and before the subject is randomised to receive the first dose of emodepside or placebo. Before giving consent, subjects must read the information sheet about the trial. They must also read the consent form. They will then discuss the trial with the Investigator, or his deputy, and be given the opportunity to ask questions. The trial-specific information sheet and the consent form must be approved by the REC.

All screened subjects will be allocated a Screening Number.

After successful screening, subjects will be enrolled, and allocated to a cohort in the trial, according to their availability and the scheduled trial dates. Subjects will be assigned Subject Numbers (in the order in which they are admitted to the ward), when they receive their first dose ('Randomised' subjects). Subject numbers in the trial will be as shown in Table 6 . Subjects will be allocated to treatment (active or placebo) according to a randomization schedule prepared by an independent HMR statistician, using a SAS program. Sufficient subjects will be screened to ensure up to 24 subjects are randomized.

7. Study treatments

Subjects in Cohorts 1–3 will be randomised to receive either emodepside LSF solution, or matching placebo solution. Subjects in Cohorts 1 and 2 will receive once-daily doses of LSF or placebo, and subjects in Cohort 3 will receive twice-daily doses of LSF or placebo, by mouth.

The planned treatments to be administered are described below in Table 6 .

7.1. Doses and treatment regimens

Randomised subjects will be given a unique ID (subject number; Table 6) that will be recorded in the case report form (CRF), and will be retained throughout the study.

This subject number will also appear on the study medication containers.

Table 6 . Study treatment: Subject numbers, Formulation, and Dose-Levels by Cohort

	Subject numbers ^a	Formulation and route of administration	Planned subjects	
			Emodepside	Matching placebo
Cohort 1	1001 – 1008	5 mg LSF solution OD, or placebo, by mouth	6	2
Cohort 2	2001 – 2008	10 mg LSF solution OD, or placebo, by mouth	6	2
Cohort 3	3001 – 3008	10 mg LSF solution BID, or placebo, by mouth	6	2

^a Any subjects who are replaced in a cohort will have the subject number incremented by 100 (eg, 1001 would be replaced by 1101)

Subjects will receive the study medication according to fasting instructions given in Section 4.3: On dosing days, following an 9 h overnight fast (no food or drink, except water), Investigator site personnel will administer study medication (active or placebo) to subjects with 240 mL ambient temperature water.

Subjects in Cohort 3 will be given an evening dose approximately 12 h after their morning dose on Days 0–9: they'll fast for 2 h before and 1 h after that evening dose.

Study treatment will be administered under the supervision of Investigator site personnel, following site standard procedures to ensure treatment compliance.

